EBIRE: Phase I Study of High Fluence LED-Red Light in Fitzpatrick Skin Types I to III

VA File Number: 18-01-00804

Funding Agency: EBIRE

Principal Investigator: [name], MS

January 12, 2018

Abstract

Objective: To determine the safety of high fluence light emitting diode-red light (HF-LED-RL) phototherapy in Fitzpatrick skin types I to III.

Research Design: This study will be a single-blind, dose-escalation, randomized controlled, Phase 1 study of HF-LED-RL in Fitzpatrick skin types I to III. Subjects with Caucasian or white skin color (Fitzpatrick skin types I, II, or III) will be enrolled sequentially in groups of five (three subjects randomized to HF-LED-RL phototherapy and two subjects randomized to mock therapy). This study is based on the results of the previous “Phase 1 study of LED-RL in Human Skin” (VA file number: 15-12-00756), which demonstrated that HF-LED-RL doses up to 320 J/cm² was safe in all skin types. One male subject with Fitzpatrick skin type V had an adverse event of a blister with HF-LED-RL at fluence of 480 J/cm². The other two subjects, who were of Fitzpatrick skin types I to III, treated with HF-LED-RL at fluence of 480 J/cm² had no adverse event. Therefore, we wanted to explore the safety of HF-LED-RL at doses of 480 J/cm² and 640 J/cm² in Fitzpatrick skin types I to III.

The initial group will receive doses of 480 J/cm² of HF-LED-RL or mock therapy at the Sacramento VA Medical Center Dermatology Clinic three times a week for three consecutive weeks, which is a standard phototherapy regimen based on phototherapy guidelines. An additional group (Group 2: 640 J/cm²) will be sequentially enrolled to receive a higher dose of HF-LED-RL phototherapy or mock therapy. If there is a single adverse event in either Group 1 or Group 2, we will repeat that same dose in a new cohort of five additional subjects (Group 1A or 2A, respectively). This is to account for a

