Our dose-escalation protocol is as follows (Figure 2): In the first group (Group 1), HF-LED-RL phototherapy or mock therapy treatment time durations associated with 480 J/cm² will be administered to five subjects. Five subjects will be enrolled with three subjects randomized to HF-LED-RL phototherapy and two subjects randomized to mock therapy. Randomization is performed with website: www.randomizer.org. The randomizer will generate arabic numerals (e.g. “1”, “2,” “3”). Each enrolled subject will undergo two randomizations. For the first randomization, “1” is Group 1, “2” is “Group 2” and “3” is Group 3. 10 subjects will be

randomized to Group 1, 10 subjects will be randomized to Group 2, and 45 subjects will be randomized to Group 3. If there are no adverse events in the first five subjects of either Group 1 or 2, then the remaining 5 subjects of the 10 subjects randomized to that group will default into Group 3. For the second randomization, "1" is HF-LED-RL phototherapy and "2" is mock therapy. This study is single-blind and subjects will be blinded to this randomization, while researchers ([name], [name], and [name]) have knowledge of all subjects' randomization for the entirety of this study.

Dose escalation starts at fluence of 480 J/cm² and continues up to fluence of 640 J/cm² until at least two subjects among a cohort of five to ten subjects experience an adverse event (i.e. >20% of subjects with an adverse event at that dose level). If there are no adverse events in the five subjects treated with HF-LED-RL or mock therapy at fluence of 480 J/cm² in Group 1, then we will escalate the dose of HF-LED-RL or mock therapy to fluence of 640 J/cm² in the next cohort of five subjects (Group 2). If there is a single adverse event with HF-LED-RL or mock therapy at fluence of 480 J/cm², we will repeat the same dose of 480 J/cm² in a new cohort of five additional subjects (Group 1A). This is to account for a possible outlier effect. If two or more subjects in the first cohort of Group 1 experiences an adverse event with HF-LED-RL or mock therapy at fluence of 480 J/cm², then the study will stop and the MTD is 320 J/cm². If there are no adverse events in Group 1A, then the dose will be escalated to 640

J/cm2 in the next cohort (Group 2). If there is an adverse event in Group 1A ($\geq 20\%$), then the study will stop and the MTD is 320 J/cm2.

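### Section 5.1 draws subjects into dose groups 10/10/45 and moves unused subjects to Group 3, which contradicts sequential cohorts of five and the stated sizes (Group 3 up to 55, not 45; final dose up to 60, not 50 or 55)

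*Combined protocol and SAP*

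**What the plan says.** The randomization paragraphs of Section 5.1 contain two schemes.

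- **Sequential cohorts.** For Group 1, "Five subjects will be enrolled with three subjects randomized to HF-LED-RL phototherapy and two subjects randomized to mock therapy". The Abstract says subjects "will be enrolled sequentially in groups of five" and, after a single event, "we will repeat that same dose in a new cohort of five additional subjects (Group 1A or 2A, respectively"). The list of group sizes in Section 5.1 likewise adds five subjects only after one event. The expansion paragraph enrolls 27 active and 18 mock subjects after the MTD or 640 J/cm² has been reached.
- **Dose-group draw.** "Each enrolled subject will undergo two randomizations". One is to dose group, with 10 subjects "randomized to Group 1, 10 subjects will be randomized to Group 2, and 45 subjects will be randomized to Group 3"; the other is to active or mock. A default rule follows. It applies when a group's first five subjects are free of adverse events, and its consequence reads "then the remaining 5 subjects of the 10 subjects randomized to that group will default into Group 3".

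The stated sizes are:

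- Groups 1 and 2: 5 or 10 each (Section 5.1, group list).
- Group 3: 27 + 18 = 45 (group list; the study timeline repeats 27 and 18).
- Final dose: 30 or 33 active and 20 or 22 mock (Abstract and Section 5.1). The Abstract adds a single total of 50.
- Whole study: 65, without condition (Section 5.1).

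**The concern.** In a sequential escalation, the next five people enrolled form the next cohort, and the outcome of the last cohort decides their dose. A random draw among three dose groups at enrolment cannot also do that. A subject drawn to Group 3 has no known dose until Groups 1 and 2 are finished. The draw could work only if Group 2 and 3 subjects were allocated early and held back. The visible text does not describe this for Group 3 (Figures 1 to 3 are not shown), and it would contradict the enrolment timing in the Abstract and the expansion paragraph.

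The default rule also changes the number of people treated at the final dose. On the no-event path ten more subjects would receive the final-dose regimen; at nine procedure visits each, that is 10 × 9 = 90 further sessions of 120 minutes. The expansion halting threshold of 30% may move as well. If its denominator is the planned Group 3 size (an assumption, since none is stated), it is met at 14 events of 45, 15 of 50 or 17 of 55.

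The rule also covers only event-free groups. If two or more of Group 2's first five have events, the other five subjects randomized to Group 2 have no stated destination.

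**Working it through.** **1. The plan's own figures.** 27 + 18 = 45. Active: 3 + 27 = 30 or 6 + 27 = 33. Mock: 2 + 18 = 20 or 4 + 18 = 22. Totals: 30 + 20 = 50 or 33 + 22 = 55. Draw: 10 + 10 + 45 = 65. The final-dose totals reproduce exactly when nobody defaults into Group 3.

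**2. Every branch that reaches the expansion.** Under the default rule, Group 3 = 45 + 5 for each of Groups 1 and 2 whose first five are event-free. Final-dose total = Group 3 plus the escalation subjects at that dose. The decision rule for Group 2A is inferred from the Group 1A rule, which begins "If there is an adverse event in Group 1A".

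| Events in Group 1 | Events in Group 2 | Group 3, default rule | Final dose, default rule | Final dose, sequential | Whole study, sequential |
|---|---|---|---|---|---|
| 0 | 0 | 55 | 60 | 50 | 55 |
| 0 | 1, then 0 | 50 | 60 | 55 | 60 |
| 0 | 1, then ≥1 | 50 | 55 | 50 | 60 |
| 0 | ≥2 | 50* | 55* | 50 | 55 |
| 1, then 0 | 0 | 50 | 55 | 50 | 60 |
| 1, then 0 | 1, then 0 | 45 | 55 | 55 | 65 |
| 1, then 0 | 1, then ≥1 | 45 | 55 | 55 | 65 |
| 1, then 0 | ≥2 | 45* | 55* | 55 | 60 |

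*Five Group 2 subjects have no destination and are left out. Placing them in Group 3 would make the final-dose total 60 in both rows.

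The Abstract's 50 is never reached under the default rule. A total of 60 exceeds 33 + 22 = 55 however the defaulted subjects split between arms.

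**3. How likely the conflicting branches are.** The documents give no planning event rate for this study. Assume one independent rate p for every subject, with a = (1−p)^5 (no event in five) and b = 5p(1−p)^4 (exactly one).

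- P(expansion reached) = a(1+b)
- P(final dose 60, given expansion) = a·a(1+b) / [a(1+b)] = a
- P(Group 3 = 45, given expansion) = b(1−a)/(1+b)
- P(five with no destination, given expansion) = 1 − a − b

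| p | Expansion reached | Final dose 60 | Group 3 = 45 | No destination |
|---|---|---|---|---|
| 1% | 0.997 | 0.951 | 0.002 | 0.001 |
| 5% | 0.931 | 0.774 | 0.038 | 0.023 |
| 10% | 0.784 | 0.590 | 0.101 | 0.081 |
| 20% | 0.462 | 0.328 | 0.195 | 0.263 |

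The final-dose total is therefore 5 or 10 above the sequential total in 99.8%, 96%, 90% and 80% of expansions. If rates differ by dose, the chance of 60 is a₂(1+b₂)/(1+b₁), with subscripts for Groups 1 and 2. With both rates at the plan's 1-in-10 target this is 0.784/1.328 = 0.590. A grid over separate active and mock rates at each dose, all at or below 10%, gives the same minimum.

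**4. Effect on the safety claim.** With zero events in n active subjects the exact 95% upper limit is 1 − 0.05^(1/n): 9.5% at n = 30, 8.7% at n = 33 and 8.0% at n = 36. The 36 assumes that defaulted subjects split 3:2, so that 60 = 36 + 24.

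**The case against.** Five points can be made for the text as it stands.

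- **The figures of 55 and 60 rest on one reading.** If 27 + 18 is a cap, defaulted subjects would fill Group 3 places rather than add to them. But 45 are randomized to Group 3 and the others default into it, so adding is the literal reading, and no cap is stated.
- **Part of a reserve mechanism is written down.** The second five of Groups 1 and 2 do wait on the outcome of the first five. That is correct, but it does not cover the 45 drawn to Group 3, nor remove the conflict with enrolling them after escalation.
- **The 65 agrees with the draw.** It equals 10 + 10 + 45, so one could keep the draw and restate Group 3 as 45, 50 or 55. That is a possible reconciliation, but the Abstract, the group list and the expansion paragraph would all need rewriting, and the waiting rule and missing destination supplied.
- **The extra subjects give a margin against dropout.** With zero events the limit is 9.8% at n = 29 but 10.15% at n = 28. Losing two of 30 active subjects would therefore break the 1-in-10 claim, if discontinued subjects are not counted (the documents do not say). This is fair, but 30 is the plan's own stated size. A wanted margin should be planned openly.
- **The branch probabilities rest on an assumed rate** and describe planned totals, before withdrawals or halting. This stands. The no-event path alone is enough to show the contradiction.

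**Conclusion.** The concern holds. The dose-group draw and default rule contradict the sequential enrolment described elsewhere, and they change the planned sizes. On the no-event path Group 3 is 55 against 45, the final dose 60 against 50, and the whole study 65 against 55. With Group 1 clear and Group 2 repeated and clear, the final dose is 60 against 55. Three further branches give 55 against 50. The last three agree on size, although one of them leaves five randomized subjects unplaced.

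Two stated totals also need correcting under sequential enrolment: the single 50 in the Abstract omits the 55 case, and the unconditional 65 in Section 5.1 is only the maximum of 55, 60 or 65.

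The counts assume that defaulted subjects are added to the 45 and that Group 2A follows the Group 1A rule. Statistical precision is not lost. The harm is that staff must choose which text to follow, and the number treated at the final dose depends on that choice. It should be fixed before enrolment.

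**What to change.** Delete the dose-group draw and the default rule from Section 5.1. Fill cohorts in enrolment order and randomize only HF-LED-RL versus mock: 3:2 within each cohort of five and 27:18 in the expansion.

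State the sizes once, by branch:

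- 5 or 10 subjects if the study stops in Group 1 or 1A.
- Otherwise 55, 60 or 65 overall, with 30 + 20 = 50 or 33 + 22 = 55 at the expansion dose.

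Amend the 50 in the Abstract and the 65 in Section 5.1 to match.

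The cost is protocol wording and a simpler randomization list. The number needed never exceeds the 65 now randomized, and it is 55 on the no-event path.

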muscle weakness), then this is the dose one above the MTD and we will not proceed with this dose or escalate the dose. The dose below the dose that generated the adverse event is the MTD. Rare but serious adverse events include second or higher degree skin burn, severe swelling, pain, ulceration, change in sensation, or muscle weakness leading to hospitalization, life-threatening events, or death.

The data safety monitoring board (DSMB) includes: [name], [name], and [name]

HF-LED-RL phototherapy and mock therapy at fluences of 480 J/cm² or 640 J/cm² will be administered to 65 subjects with Caucasian (white) skin types (Fitzpatrick skin types I, II, and III) to determine safety of HF-LED-RL at fluences of 480 J/cm² and 640 J/cm² in Fitzpatrick skin types I, II, and III. Because up to 320 J/cm² HF-LED-RL was found to be safe in all Fitzpatrick skin types (unpublished data from “previous Phase 1 LED-RL study”), this study will study 480 J/cm² and 640 J/cm² in Fitzpatrick skin types I, II, and III based on Spilker’s dose escalation protocol (X=160 J/cm², 2X=320 J/cm², 3X = 480 J/cm², and 4X = 640 J/cm²).

Number of subjects in each group:

Group 1 (480 J/cm²; 3 or 6 HF-LED-RL phototherapy subjects and 2 or 4 mock therapy subjects) - Total 5 or 10 subjects

Group 2 (640 J/cm²; 3 or 6 HF-LED-RL phototherapy subjects and 2 or 4 mock therapy subjects) - Total 5 or 10 subjects

Group 3 (480 or 640 J/cm² depending on dose escalation algorithm; 27 HF-LED-RL phototherapy subjects and 18 mock therapy subjects) - Total 45 subjects

* If there is one adverse event in one subject in either Group 1 or 2, five additional subjects will be added to that group (3 will receive HF-LED-RL and 2 will receive mock therapy).

We based our dose escalation protocol for this new study on a similar Phase 1 dose escalation study design outlined in the Journal of National Cancer Institute (Le Tourneau et al 2009), to determine dose escalation and to account for a possible outlier effect in the treatment group. Dose escalation starts at fluence of 480 J/cm² and continues up to fluence of 640 J/cm² until at least two subjects among a cohort of five to ten subjects experience an adverse event (i.e. $\geq 20\%$ of subjects with an adverse event at that dose level).

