After either a MTD has been established or the study endpoint of 640 J/cm2 has been achieved, an additional 27 HF-LED-RL phototherapy subjects (for a total of 30 or 33) and 18 mock therapy (for a total of 20 or 22) (determined randomly) will be enrolled to satisfy Hanley's Rule of Three, such that it can be concluded with 95% confidence that fewer than 1 person in 10 will experience an adverse event (Figure 3). (Hanley 1983) If the MTD is 320 J/cm2, then the study will be stopped and no further testing of the MTD of 320 J/cm2 in the larger cohort will be indicated because the MTD of 320 J/cm2 was already tested in a large cohort in the "previous Phase 1 LED-RL study". Of the larger expansion cohort, the study will be halted (stopped) if adverse events determined to be device related equals or exceeds 30%.

This clinical trial will be registered on <https://clinicaltrials.gov> following IRB approval and prior to subject enrollment.

- The subject will receive standard of care treatment in the dermatology clinic for any adverse event. Physical examination/visual inspection of the treated forearm will occur at every study visit. Treatment will be initiated, if indicated, for any procedural outcomes or adverse events noted at every study visit. Any general dermatology adverse events will be managed by [name] in the Dermatology clinic, per standard of care. If a skin ulcer occurs, we will record the skin ulceration as a superficial ulceration

(meaning it is nearly flush with the skin) or, if measurable, the depth of ulceration in millimeters. If skin ulceration occurs, we will consult [name], who is an expert in wound healing and head of the Sacramento VA wound clinic, for management. If change in sensation or muscle weakness occurs in a subject, the subject will be sent to Sacramento VA Emergency Room for urgent grading and management. If there are any other adverse events that cannot be managed in the Dermatology clinic, the subject will be sent to the Sacramento VA Emergency Room for urgent care.

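### The arm is assigned by a per-subject draw with no list, weighting or concealment described, although the plan needs exact 3:2 and 27:18 counts

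*Combined protocol and SAP*

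**What the plan says.** Section 5.1 (Study Design) sets out the mechanism in three statements: "Randomization is performed with website: www.randomizer.org"; "Each enrolled subject will undergo two randomizations", the first for the group and the second for the arm; and "For the second randomization, '1' is HF-LED-RL phototherapy and '2' is mock therapy". It does not give the chance of each numeral, a list or its length, a blocking rule, a holder of the list, or any concealment. Subjects are blinded. The three named researchers know every subject's allocation for the whole study.

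The required counts are exact:
- Abstract: subjects are "enrolled sequentially in groups of five (three subjects randomized to HF-LED-RL phototherapy and two subjects randomized to mock therapy".
- Section 5.1, Group 1: "Five subjects will be enrolled with three subjects randomized to HF-LED-RL phototherapy and two subjects randomized to mock therapy".
- Section 5.1, after a single adverse event: "five additional subjects will be added to that group (3 will receive HF-LED-RL and 2 will receive mock therapy".
- Section 5.1, expansion: "an additional 27 HF-LED-RL phototherapy subjects (for a total of 30 or 33) and 18 mock therapy (for a total of 20 or 22".

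Section 5.1 also says that, if the first five subjects of Group 1 or Group 2 have no adverse event, the other five drawn to that group pass to Group 3 by default. It does not say how their arm is set.

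**The concern.** A separate draw for each subject and a fixed split are different procedures, and the text describes the first while requiring the second.

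If the draws are taken literally, the arm sizes vary by chance. The escalation rule counts adverse events among all five subjects whatever their arm, so a dose could be cleared with few subjects exposed to light. The expansion is meant to support a 95% statement that fewer than 1 person in 10 will have an adverse event, and that rests on about 30 HF-LED-RL subjects.

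If the split is enforced, the later places in a small cohort follow from the earlier ones, and the team that knows the earlier ones also screens (Section 5.1). Entry involves some judgement: the failure criteria for the photosensitivity test in Section 5.5 are expressly not exhaustive. Section 2.0 proposes that melanin raises sensitivity to red light, and Section 5.4 says that type I, II or III will not be documented. If foreknowledge influenced who entered which arm, the resulting imbalance would be hard to see in the data.

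**Working it through.** **Stated totals.** HF-LED-RL: 3 + 27 = 30 or 6 + 27 = 33. Mock: 2 + 18 = 20 or 4 + 18 = 22. These match Section 5.1, so the plan intends a fixed 3:2 ratio throughout.

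**Reading A: separate draws.** The draw probability p for HF-LED-RL is not stated. I assume 0.5 (two numerals, equal chance) and 0.6 (weighted to the intended ratio). With X binomial, P(X = k) = C(n,k) p^k (1−p)^(n−k).

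| Event | p = 0.5 | p = 0.6 |
|---|---|---|
| Exactly 3 of 5 on HF-LED-RL | 10 × 0.5^5 = 0.3125 | 10 × 0.6^3 × 0.4^2 = 0.3456 |
| Two or fewer of 5 on HF-LED-RL | 0.500 | 0.317 |
| Exactly 27 of 45 in Group 3 | 0.049 | 0.121 |
| 30 or more of 50 at the final dose | 0.101 | 0.561 |

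The 50 are one cohort of five plus the 45 of Group 3. With no adverse events, the exact one-sided 95% upper bound is 1 − 0.05^(1/n). For n = 30 it is 9.5%, which supports the 1-in-10 statement. For n = 25, the expected number at p = 0.5, it is 11.3%, which does not.

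**Reading B: a restricted list.** The counts are then exact. Suppose the team knows the ratio and the assignments already made. A place is certain in advance once one arm is full. Of the 10 orderings of three HF-LED-RL and two mock, 6 fix only the last place, 3 fix the last two and 1 fixes the last three:

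(6×1 + 3×2 + 1×3) / 10 = 15/10 = 1.5 of 5, or 30%.

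The general formula for a list of a and b gives the same: a/(b+1) + b/(a+1) = 3/3 + 2/4 = 1.5. Always guessing the arm with more places left is right for 3.6 of 5 (72%) on average, against 60% for always naming HF-LED-RL.

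For one 27:18 list in Group 3: 27/19 + 18/28 = 1.421 + 0.643 = 2.06 of 45 (4.6%) are certain in advance. Best-guess accuracy is 63%.

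**Trial-wide share under Reading B.**
- Two cohorts of five plus one 27:18 list: (2×1.5 + 2.06)/55 = 9.2%.
- Four cohorts of five plus that list: (4×1.5 + 2.06)/65 = 12.4%.
- Group 3 also filled in fives: 30% throughout.

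**Default to Group 3.** If neither Group 1 nor Group 2 has an event, 5 + 5 subjects pass to Group 3. Added to the 45 drawn there, that is 55, against the 45 stated.

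**The case against.** The strongest reply is that independent draws are an assumption. The sentence on the second randomization may be no more than a code key, and the same section fixes the counts. A shuffled list of three 1s and two 2s fits the wording, and on that reading none of the binomial figures applies. This stands. A reader might infer that the counts can be met only if the team stops drawing when an arm is full and fills the rest by default. The documents do not support that, because a shuffled list meets them too.

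A reader might also take 30% as the share of all assignments that is predetermined. Section 5.1 presents Group 3 as one cohort of 45 with no sub-blocks. Only the Abstract's general phrase about groups of five suggests otherwise.

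Foreseeability also depends on the reading. If the group draw decided a subject's cohort in no fixed order, staff might not know which cohort comes next. However, the Abstract describes sequential enrolment, and escalation to Group 2 depends on the result of Group 1. In the other direction, if knowing all allocations includes future ones, every place is foreseeable.

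Finally, biased entry is hypothetical. All subjects are meant to be types I to III, the arm is drawn for subjects already enrolled, escalation counts events in both arms together, and Section 5.6 plans frequencies without a between-arm test. This limits the likely effect. It does not remove it, because Section 2.0 uses the contrast between light and mock to attribute events to light or to heat.

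**Conclusion.** The concern holds as a mismatch between the described mechanism and the required counts, together with missing concealment. Each reading leaves a defect. Separate draws give exactly 3:2 in only 31% to 35% of cohorts and 30 or more HF-LED-RL subjects of 50 in 10% to 56% of trials, for assumed draw probabilities of 0.5 and 0.6. A restricted list secures the counts but leaves an average of at least 1.5 of 5 places foreseeable in each escalation cohort, given sequential enrolment and knowledge of past assignments. Across the trial that is about 9% to 12% with one Group 3 list, and 30% only if Group 3 is also filled in fives.

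A reader might go further and conclude that recruitment will be steered so that the light looks safer. Nothing in the documents shows this or suggests intent; the plan simply describes no safeguard against it. The point is worth acting on because the change is almost free and secures the counts behind the dose decisions and the 1-in-10 statement.

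**What to change.** In Section 5.1, replace the per-subject arm draw with lists generated in advance on the same website:
- One shuffled 3:2 list for each escalation cohort of five, including any repeat cohort.
- One shuffled 27:18 list for all of Group 3, not blocks of five.
- Keep the lists in numbered sealed envelopes, or with an existing staff member who does not recruit. The documents available do not identify such a person, so envelopes may be the practical choice.
- Open each assignment only after the Visit 2 eligibility decision has been recorded.
- Limit the researchers' knowledge to assignments already made.
- State that unused Group 1 or Group 2 subjects who default to Group 3 take their arm from the Group 3 list, within its 45 places.

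The cost is one paragraph and a few minutes of list generation, with no added subjects or visits. In Group 3, compared with filling it in fives, certain places fall from 30% to 4.6% and best-guess accuracy from 72% to 63%.

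There are two drawbacks. The Group 3 ratio may drift from 3:2 partway through, although it ends at 27:18. The last places in each cohort of five remain inferable from the ratio and the earlier assignments, so the change reduces predictability there but does not remove it.

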5.0 Study Procedures

5.1 Study Design

- This is a single-blind, randomized, ascending dose escalation Phase I study of HF-LED-RL in healthy subjects with Fitzpatrick skin types I to III to evaluate safety of HF-LED-RL in Fitzpatrick skin types I to III (Figure 1). The study endpoint of 640 J/cm² is due to feasibility, as this dose corresponds to two hours of HF-LED-RL irradiation, and we anticipate decreased subject compliance with HF-LED-RL exposures longer than 2 hours in duration. The study endpoint of 640 J/cm² was also selected as this dose demonstrated increased anti-fibrotic properties in vitro compared to lower doses of HF-LED-RL (Mamalis 2015). Subjects will receive HF-LED-RL phototherapy or mock therapy three times a week for

three consecutive weeks, which is a standard phototherapy regimen based on phototherapy guidelines (Anderson et al 2015, Menter et al 2010, Zanolli et al 2004).

The HF-LED-RL light source is a commercially available Omnilux New-U hand-held LED-RL phototherapy unit (provided by Photo Therapeutics, Carlsbad, CA, USA), and is FDA-cleared for treatment of periorbital rhytides (crow's feet) with doses up to 160 J/cm². The temperature-matched mock therapy unit, also provided by Photo Therapeutics, Carlsbad, CA, USA, generates only heat output comparable to heat generated by the HF-LED-RL device, which is less than two degrees Celsius of heat output, and does not emit HF-LED-RL.

We do not classify erythema (redness) lasting less than 24 hours as an adverse event in our study, and is expected to occur in at least 10% of subjects as previously demonstrated in published studies (Sadick 2008, Sadick 2008). Common expected procedure outcomes include: warmth, erythema (redness), and edema (swelling) that is expected to last less than 24 hours.

- The maximum tolerated dose (MTD) is defined as the dose level below the dose producing unacceptable but reversible toxicity in two or more subjects ($\geq 20\%$) and is considered the upper limit of subject tolerance. If two or more subjects experiences any adverse event (including: first-degree or higher skin burning or blistering, erythema lasting more than 24 hours, swelling, pain, ulceration, infection, change in sensation, and/or

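### The percentages attached to the MTD definition and escalation rule do not match the two-subject count they claim to restate: they part at 1 of 5 and 2 of 10

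*Combined protocol and SAP*

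**What the plan says.** All of this is in section 5.1, Study Design, unless noted.

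- **MTD definition.** The MTD is the level below the one "producing unacceptable but reversible toxicity in two or more subjects ($\geq 20" (a percent sign completes the bracket). The Abstract gives the same definition by count alone, with no percentage.
- **Escalation sentence, first occurrence** (after the list of group sizes). Escalation goes on "until at least two subjects among a cohort of five to ten subjects experience an adverse event", explained as "i.e. $\geq 20\%$ of subjects with an adverse event at that dose level".
- **Escalation sentence, second occurrence** (in the dose-escalation protocol paragraphs). The same sentence, now explained as "i.e. >20% of subjects with an adverse event at that dose level".
- **Cohort sizes.** Groups 1 and 2 are each planned as "3 or 6 HF-LED-RL phototherapy subjects and 2 or 4 mock therapy subjects) - Total 5 or 10 subjects".
- **Steps at 480 J/cm².** After one event, "we will repeat the same dose of 480 J/cm² in a new cohort of five additional subjects (Group 1A"). Two or more events in the first cohort stop the study with an MTD of 320 J/cm². No event in Group 1A leads to 640 J/cm². The stopping sentence for the repeat cohort opens "If there is an adverse event in Group 1A" and carries its own bracketed at-least-20% figure.
- **Steps at 640 J/cm².** The Abstract and section 5.1 add five subjects after a single event in Group 2. The text available does not go on to say what each Group 2A result means.

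**The concern.** The percentage is offered as another way of saying two or more subjects. If the two differ at a result the design can produce, the MTD definition and the escalation rule each carry two thresholds. The planned sizes are 5 and 10, and 1 of 5 and 2 of 10 are the results on which these rules turn.

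At stake are how the MTD is declared at 640 J/cm² and, through it, whether Group 3 (27 active + 18 mock = 45 subjects) is treated at 480 or 640 J/cm². Section 5.1 also says the researchers know every allocation throughout, which is a further reason to have one reading fixed before data are seen.

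**Working it through.** **Inputs**

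- Stopping count: x ≥ 2 subjects with an event (section 5.1; Abstract).
- Percentage, version A: x/n ≥ 20% (MTD definition and first escalation sentence).
- Percentage, version B: x/n > 20% (second escalation sentence).
- n = 5, or 10 after expansion, with mock subjects included (section 5.1, group sizes).
- Event probability p per subject: **assumed**, 0.10 to 0.20, equal in both arms and independent between subjects. The documents give no value.

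**Step 1. Do the percentages reproduce the count?**

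| Result | Rate | Count (≥ 2) | A (≥ 20%) | B (> 20%) |
|---|---|---|---|---|
| 1 of 5 | 20% | not met | **met** | not met |
| 2 of 5 | 40% | met | met | met |
| 1 of 10 | 10% | not met | not met | not met |
| 2 of 10 | 20% | met | met | **not met** |
| 3 of 10 | 30% | met | met | met |

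Version A departs from the count at 1 of 5. Version B departs from it at 2 of 10. For sizes between, A agrees with the count from n = 6 to 10 (1/6 = 16.7% is below 20%; 2/10 = 20% reaches it). B agrees from n = 5 to 9 (2/9 = 22.2%). Each fails at one of the two sizes the design uses.

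**Step 2. The bracket in the Group 1A sentence.** One event in Group 1A is 1/5 = 20% of that cohort, or 2/10 = 20% of the pooled ten. The sentence does not say which denominator it means. If it means five, at least 20% stands for one subject here and for two in the MTD definition.

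**Step 3. Which results have an explicit step?**

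| Result | 480 J/cm² | 640 J/cm² |
|---|---|---|
| 1 of 5 | repeat cohort (1A) | five more subjects (2A) |
| 1 of 5, then 0 of 5 | escalate | no step in the text |
| 1 of 5, then 1 of 5 | stop, MTD 320 J/cm² | no step; general sentences only |

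In the last cell, the count and version A put 640 J/cm² above the MTD, which would send Group 3 to 480 J/cm². Version B, taken alone, would not.

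**Step 4. How often are the boundary results reached?**

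P(1 of 5) = 5p(1 − p)⁴
- p = 0.10: 5 × 0.10 × 0.6561 = 0.328
- p = 0.20: 5 × 0.20 × 0.4096 = 0.410

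P(1 of 5, then 1 of 5) = the square of that
- p = 0.10: 0.3281² = 0.108
- p = 0.20: 0.4096² = 0.168

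**Step 5. How far apart are the rules if each is applied literally?** Write P0 = (1 − p)⁵ (0.5905 at p = 0.10; 0.3277 at p = 0.20) and P1 = P(1 of 5). The probability that a dose level passes is:

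| Reading | Formula | p = 0.10 | p = 0.20 |
|---|---|---|---|
| Stepwise count | P0 + P1·P0 | 78.4% | 46.2% |
| A alone | P0 | 59.0% | 32.8% |
| B alone | P0 + P1·(P0 + P1) | 89.2% | 63.0% |

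The gap between B and the stepwise count is P1², the 10.8% and 16.8% of step 4. This table measures how far the statements disagree. It does not predict conduct, because at 480 J/cm² the explicit steps would govern.

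**The case against.** The strongest defence is that the operative rule is a count throughout. The Abstract has no percentage. Each percentage sits in a bracket behind a count or event condition, and two or more out of five to ten is indeed never less than 20%. Read as a description, version A is true; it conflicts at 1 of 5 only when used as a test in its own right. The second sentence also says at least two subjects in its own words, and 2 of 10 satisfies that. Finally, the > sign may be a ≥ that lost its underline when the PDF was read.

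Much of this stands. A reader might infer that the threshold is undefined, or that opening 640 J/cm² could be argued either way after the data are seen. The documents do not support that: section 5.1 assigns an action to 1 of 5 and to 1 of 5 followed by another event at 480 J/cm², and the add-five rule covers 1 of 5 at 640 J/cm².

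What remains is that the escalation sentences present the percentage as equivalent to the count, and at n = 5 version A is not. This does not depend on the > sign. If that sign is an extraction loss, only the 2 of 10 disagreement falls away. At 640 J/cm² after Group 2A, the general sentences are all the text offers, although Figure 2 may contain the missing steps.

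**Conclusion.** The point holds as a mis-stated threshold inside the MTD definition and the escalation rule. The 1 of 5 mismatch is certain on the text. The 2 of 10 mismatch is conditional on the > sign being what the protocol prints.

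The practical effect differs by dose. At 480 J/cm² it is limited to general wording that contradicts clear steps. At 640 J/cm² it is larger: the count does cover 2 of 10, but it appears in the same sentence as a percentage that may say otherwise, and the result determines the dose for Group 3.

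Under the assumed 10% to 20% event rate, 1 of 5 arises with probability 33% to 41% and 1 of 5 twice with probability 11% to 17%. A reader might take these as the chance that the decision changes. They are only the chance of reaching a result at which the statements differ, and they rest on a common rate in active and mock subjects that the documents do not give.

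**What to change.** State the escalation and MTD rule once, in counts, for a cohort of 5 and for a pooled cohort of 10, and cover Group 1/1A and Group 2/2A in the same form. Then delete or correct the percentage in its four places in section 5.1: the MTD definition, both occurrences of the escalation sentence, and the Group 1A sentence. If a percentage is kept, name its denominator. Check that Figure 2 says the same.

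Which threshold is clinically right is for the investigator; the request is only that the statements be reconciled. The cost is a wording change, with no effect on sample size, visits or conduct.
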